8.2 Data Analysis	28
8.2.1 Analysis Sets	28
8.3 Effectiveness	29
8.3.1 Effectiveness Variables	29
8.3.2 Methods of Analysis	29
8.4 Safety	30
8.4.1 Safety Variables / Criteria	30
8.4.2 Methods of Analysis	30
8.5 Interim Analyses.....	30

8.6	Handling of Missing Data	30
9	SAFETY DEFINITIONS.....	30
9.1	Adverse event.....	30
9.1.1	Suspected adverse reaction	30
9.1.2	Adverse reaction	31
9.2	Serious Adverse Event.....	31
9.2.1	Life threatening.....	31
9.2.2	Unexpected	31
9.3	Suspected unexpected serious adverse reaction (SUSAR)	31
9.4	Relationship	32
9.5	Severity	32
9.6	Collection of Adverse Events	32
9.7	Adverse Event Reporting	33
10	REGULATORY OBLIGATIONS	33
10.1	Informed Consent	33
10.2	Institution Approval / Ethics Committees.....	33
10.3	Data Management	33
10.3.1	Data Collection	33
10.3.2	Data Correction.....	34
10.4	Sponsor Obligations	34
10.4.1	Monitoring	34
10.4.2	Regulatory Requirements	34
10.4.3	Liability and Insurance Conditions	35
11	INVESTIGATOR OBLIGATIONS	35
11.1	Audit and Inspection	35
11.2	Confidentiality of Subject Records.....	35
11.3	Record Retention	35
12	CHANGES TO THE PROTOCOL	35
12.1	Protocol Amendments	35
12.2	Clinical Trial Termination.....	35
12.3	Use of Information and Publication.....	35
13	ETHICON CONTACT DETAILS	37
14	REFERENCES.....	38

A Prospective, Randomised, Controlled, Study Evaluating the Safety and Effectiveness of EVARREST Sealant Matrix in Controlling Mild or Moderate Hepatic Parenchyma or Soft Tissue Bleeding During Open, Abdominal, Retroperitoneal, Pelvic and Thoracic (non-cardiac) Surgery in Paediatric Patients

SYNOPSIS

OBJECTIVES: To evaluate the safety and haemostatic effectiveness of EVARREST Sealant Matrix (EVARREST Fibrin Sealant Patch) (EVARREST) in controlling mild or moderate soft tissue & parenchymal bleeding during open hepatic, abdominal, pelvic, retroperitoneal, and thoracic (non-cardiac) surgery in paediatric patients.

STUDY DESIGN: This is an open label, prospective, randomised, multicentre, controlled, clinical study comparing EVARREST to SURGICEL (oxidized regenerated cellulose (ORC)) (Control) as an adjunct to haemostasis when conventional methods of controlling mild or moderate bleeding are ineffective or impractical during surgery in paediatric patients.

At least 40 qualified paediatric subjects with an appropriate mild or moderate bleeding Target Bleeding Site (TBS) will be randomised in a 1:1 allocation ratio to either EVARREST or SURGICEL (control). Absolute time to haemostasis will be assessed as well as haemostasis at 4 and 10 minutes from randomisation.

Enrolment will be staggered by age (as required by the European Medicines Agency (EMA) Paediatric Committee). The first 36 subjects enrolled will be aged ≥ 1 years to <18 years of age. Enrolment of a subsequent group will include 4 subjects from 1 month (≥ 28 days from birth) to <1 year of age will follow. Ongoing safety assessment will ensure adequate safety monitoring occur during the staged enrolment.

Subjects will be followed post-operatively through hospital discharge and at 30 days (+/-14 days) post-surgery.

TBS DEFINITION: The Target Bleeding Site (TBS) will be defined as the first accessible mild or moderate bleeding site identified in the hepatic parenchyma or soft tissue, where conventional methods of controlling bleeding are ineffective or impractical, and is amenable to manual compression. The TBS must be a site where occlusion of the injured tissue surface blood vessels is required to achieve haemostasis.

The TBS must be an area that can have firm pressure applied and maintained continuously until 4 minutes after randomisation, and to which EVARREST can be applied with a margin of 1-2cm. (Refer to Investigator's Brochure).

EVARREST should not be used on large defects in arteries or veins where the injured vascular wall requires repair with maintenance of vessel patency and which would result in persistent exposure of the EVARREST to blood flow and pressure during healing and absorption of the product. EVARREST should not be used in place of sutures or other forms of mechanical ligation for the primary treatment of major arterial bleeding.

BLEEDING

SEVERITY:

Mild Bleeding: a TBS with a small area of capillary, arteriole or venule oozing

Moderate Bleeding: a TBS with a larger area of capillary, arteriole, or venule oozing that presents a significant challenge because of the larger area involved, increasing the volume of blood loss,

Or

A TBS with bleeding that is more pronounced than oozing, that could also come from a small artery or vein, but is not massive.

Severe Bleeding (EXCLUDED FROM THIS PROTOCOL): (arterial, venous, or mixed) that is rapidly flowing, pulsatile or spurting that in the surgeon's judgment requires rapid control to prevent hemodynamic consequences (e.g. hypovolemia, tachycardia, or hypotension) and could involve major volume loss which if not treated rapidly could be life threatening. EVARREST or SURGICEL should not be used in place of sutures or other forms of mechanical ligation for the treatment of major arterial bleeding.

PROCEDURE:

The TBS will be identified during the dissection related to the primary operative procedure. This will be the site assessed for haemostatic effectiveness.

Once the TBS is identified, the surgeon will immediately randomise the subject into the study. The randomly assigned treatment (EVARREST or SURGICEL) will be applied immediately at the actively bleeding TBS. The size of the treatment article applied should be sufficient for coverage of the entire TBS, and should overlap the bleeding source with a margin of 1-2 cm.

Randomised Subjects

After placement of the assigned study treatment (EVARREST or SURGICEL), firm manual continual manual compression will be applied over the entire bleeding area until 4 minutes from randomisation. The surgeon may use a surgical sponge (laparotomy pad or surgical gauze) to assist in providing adequate pressure over the entire surface area.

Haemostasis is defined as no detectable bleeding at the TBS. Absolute time to haemostasis, defined as the absolute time elapsed from randomisation to the last moment in time at which detectable bleeding at the TBS is observed, will be recorded.

Haemostasis will be assessed at 4 minutes from randomisation by carefully releasing manual compression and removing the surgical sponge (if used). Haemostasis will also be assessed at 10 minutes from randomisation and absolute time to haemostasis will be recorded.

For patients assigned to EVARREST, the EVARREST should not be removed once bleeding has been stopped.

For all subjects, if bleeding requiring treatment occurs after the 4 minute assessment the surgeon can revert to their standard of care for treatment.

Additional Treatment Impact on the Success/Failure of Endpoints

- Any additional treatment at the TBS after the 4 minute endpoint will be considered a failure for the 4 minute secondary endpoint.
- Any additional treatment after the 10 minute time point will be considered a failure for the 10 minutes secondary endpoint.

Any EVARREST re-treatment must be performed according to the Investigator's Brochure.

All subjects will have haemostasis assessed at 10 minutes after randomisation and have absolute time to haemostasis recorded regardless of any additional treatments.

EVARREST can only be used on a single TBS to be evaluated. If additional soft tissue or hepatic parenchymal bleeding sites are identified, the surgeon should treat according to their standard of care.

TEST PRODUCT: EVARREST Sealant Matrix/ EVARREST Fibrin Sealant Patch

STUDY

POPULATION:

Paediatric subjects, undergoing non-emergent abdominal, retroperitoneal, pelvic, hepatic or thoracic (non-cardiac) surgery procedures, wherein an appropriate TBS is identified. For this study paediatric subjects for this study are defined as; Infants and toddlers (28 days (1 month) from birth to 23 months), Children (2 to 11 years) and Adolescent (12 to less than 18 years).

New born infants (0-27 days from birth) are excluded from this study. Pre-term births are excluded from this protocol until the subject reaches 28 days from 37 weeks of pregnancy as determined by the investigator.

PRIMARY

ENDPOINT: Absolute time to haemostasis defined as the absolute time elapsed from randomisation to the last moment in time at which detectable bleeding at the TBS is observed.

SECONDARY

ENDPOINTS:

- Proportion of subjects achieving haemostatic success at 4 minutes following randomisation and no bleeding requiring treatment at the TBS occurs any time prior to final fascial closure
- Proportion of subjects achieving haemostatic success at 10 minutes following randomisation and no bleeding requiring treatment at the TBS occurs any time prior to final fascial closure
- Proportion of subjects with no re-bleeding at the TBS
- Incidence of adverse events that are potentially related to bleeding at the TBS;
- Incidence of adverse events that are potentially related to thrombotic events;
- Incidence of re-treatment at the TBS;
- Incidence of adverse events
- Summarization of Haemoglobin, Haematocrit, Platelets laboratory results, volume of blood loss, & volume of blood and blood products transfusions

SAFETY:

Adverse events will be collected from time of randomisation, throughout the follow-up period. Intra-operative bleeding at the TBS after 10 minutes will be an adverse event.

The following data will also be collected: laboratory tests (including Haemoglobin, Haematocrit, Platelets), volume of blood loss and volume of blood product transfused.

STATISTICAL ANALYSIS:

Sample size of 40 subjects is considered adequate to summarize data descriptively. The continuous data will be summarized by number of subjects, mean, median and standard deviation (SD). The categorical data will be summarized by frequency along with associated percentages. Two-sided 95% confidence intervals (CIs) for median absolute time to haemostasis will be reported separately for EVARREST and SURGICEL groups. In addition, for success/failure secondary endpoints (4 and 10 minutes haemostasis endpoints), two-sided 95% CI will be reported for P_F , P_C and for ratio P_F / P_C where P_F is the proportion of success in EVARREST subjects and P_C is the proportion of success in control subjects. The lower limits of these 95% CI will be utilized for statistical inferences.

SAMPLE SIZE: At least 40 randomised subjects.

Surgical Procedures: Open surgical procedures with challenging mild or moderate hepatic parenchyma or soft tissue target bleeding sites.

The surgical procedures must be open procedures, to allow for appropriate EVARREST application. When patients are undergoing abdominal and thoracic (non-cardiac) procedures, open is defined as the opening of the peritoneum or pleura. The following surgical procedures are permitted to be included in this study:

- Hepatic
- Intra-Abdominal
- Intra-Thoracic (Non-Cardiac)
- Retroperitoneal
- Pelvic (Extra-peritoneal space)

Laparoscopic, thoracoscopic and other endoscopic procedures are excluded from this study.

Soft Tissue includes but may not be limited to the following tissue types:

- Muscle
- Lymph node beds
- Lymphatic Tissue
- Fat
- Loose Areolar Connective Tissue

The study will target to have approximately a minimum of 25% of procedures with the target bleeding site in the hepatic parenchyma and approximately a minimum of 25% of procedures with the target bleeding sites in soft tissue. Enrolment will be monitored by the sponsor and the Investigators will be notified by the sponsor once those targets have been met.

Inclusion Criteria

Pre-operative:

1. Paediatric subjects aged ≥ 28 days (≥ 1 month) to <18 years, requiring non-emergent open hepatic, abdominal, retroperitoneal, pelvic or thoracic (non-cardiac) surgical procedures;
 - i) The first 36 subjects to be enrolled will be subjects aged ≥ 1 years to <18 years.
 - ii) The next 4 subjects to be enrolled will be subjects aged ≥ 28 days to <1 year.
2. The subject's parent/legal guardian must be willing to give permission for the subject to participate in the trial, and provide written Informed Consent for the subject. In addition, assent must be obtained from paediatric subjects who possess the intellectual and emotional ability to comprehend the concepts involved in the trial. If the paediatric subject is not able to provide assent (due to age, maturity and/or inability to intellectually and/or emotionally comprehend the trial), the parent/legal guardian's written Informed Consent for the subject will be acceptable for the subject to be included in the study.

Intra-operative

3. Presence of an appropriate mild or moderate bleeding soft tissue or hepatic parenchyma Target Bleeding Site (TBS) identified intra-operatively by the surgeon;
4. Ability to firmly press trial treatment at TBS until 4 minutes after randomisation;

Exclusion Criteria

Pre-operative

1. Subjects with known intolerance to blood products or to one of the components of the study product or is unwilling to receive blood products;
2. Female subjects, who are of childbearing age (i.e. adolescent), who are pregnant or nursing;
3. Subject is currently participating or plans to participate in any other investigational device or drug without prior approval from the Sponsor;
4. Subjects who are known, current alcohol and/or drug abusers
5. Subjects admitted for trauma surgery
6. Subjects with any pre or intra-operative findings identified by the surgeon that may preclude conduct of the study procedure.

Intra-operative

7. Subject with TBS in an actively infected field (Class III Contaminated or Class IV Dirty or Infected)¹
8. TBS is from large defects in arteries or veins where the injured vascular wall requires repair with maintenance of vessel patency and which would result in persistent exposure of the EVARREST or SURGICEL to blood flow and pressure during healing and absorption of the product;
9. TBS with major arterial bleeding requiring suture or mechanical ligation;
10. Bleeding site is in, around, or in proximity to foramina in bone, or areas of bony confine.

¹ Appendix 1

SCHEDULE OF EVENTS

Procedures	Screening (within 21 days prior to procedure) ⁵	Baseline (within 24 hours prior to procedure)	Surgical Procedure	Post- Surgery to Hospital Discharge	30-Day Follow Up (+/- 14 days)
Inclusion/ Exclusion	X	X	X		
Informed Consent / Assent (as applicable)	X				
Demographics	X				
Medical and Surgical History	X	X²			
Concomitant Medications		X	X	X	X
Physical Exam (including height and weight)	X			X	X
Full Blood Count with Differential	X³	X³		X	
Coagulation (PT, aPTT, INR)	X³	X³		X	
Pregnancy Tests (if applicable)		X³			
Randomisation			X		
Treatment Application and Haemostasis assessment			X		
Determination of Haemostasis at TBS			X		
Operative/Surgical information ⁴			X	X	
Assessment of bleeding or thrombotic events			X	X	X
Adverse Events			X	X	X

² Review for changes in medical history from screening visit and preform pregnancy test (if applicable)

³ At least one FBC with differential and coagulation parameter are needed pre-procedure. If pre-operative blood tests are repeated, the blood test closest to the date prior to surgery will be used.

⁴ Including length of stay, blood loss and transfusion information.

⁵ May be combined with Baseline visit

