3. OVERVIEW OF STUDY DESIGN

This is an open-label, randomised, multicentre controlled, study evaluating the safety and effectiveness of the EVARREST compared with SURGICEL in controlling mild or moderate bleeding in hepatic parenchyma or soft tissue for which standard methods of achieving haemostasis are ineffective or impractical

Eligible subjects will be randomised in a 1:1 allocation ratio to either EVARREST or SURGICEL treatment. Subjects will be followed post-operatively through discharge and at 30 days (+/-14 days) post-surgery.

Enrolment will be staggered by age. The first group enrolled will include subjects ≥ 1 years to <18 years of age and the subsequent group will include subjects from 1 month (≥ 28 days from birth) to <1 years of age. Ongoing safety assessment will ensure adequate safety monitoring occur during the staged enrolment.

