4.2 Inclusion Criteria

Pre-operative:

1. Paediatric subjects aged ≥ 28 days (≥ 1 month) to <18 years, requiring non-emergent open hepatic, abdominal, retroperitoneal, pelvic or thoracic (non-cardiac) surgical procedures;
 - i) The first 36 subjects to be enrolled will be subjects aged ≥ 1 years to <18 years.
 - ii) The next 4 subjects to be enrolled will be subjects aged ≥ 28 days to <1 year.
2. The subject's parent/legal guardian must be willing to give permission for the subject to participate in the trial, and provide written Informed Consent for the subject. In addition, assent must be obtained from paediatric subjects who possess the intellectual and emotional ability to comprehend the concepts involved in the trial. If the paediatric subject is not able to provide assent (due to age, maturity and/or inability to intellectually and/or emotionally comprehend the trial), the parent/legal guardian's written Informed Consent for the subject will be acceptable for the subject to be included in the study.

Intra-operative

3. Presence of an appropriate mild or moderate bleeding soft tissue or hepatic parenchyma Target Bleeding Site (TBS) identified intra-operatively by the surgeon;
4. Ability to firmly press trial treatment at TBS until 4 minutes after randomisation;

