4.3 Exclusion Criteria

Pre-operative

1. Subjects with known intolerance to blood products or to one of the components of the study product or is unwilling to receive blood products;
2. Female subjects, who are of childbearing age (i.e. adolescent), who are pregnant or nursing;
3. Subject is currently participating or plan to participate in any other investigational device or drug without prior approval from the Sponsor;

4. Subjects who are known, current alcohol and/or drug abusers
5. Subjects admitted for trauma surgery
6. Subjects with any pre or intra-operative findings identified by the surgeon that may preclude conduct of the study procedure.

Intra-operative

7. Subject with TBS in an actively infected field (Class III Contaminated or Class IV Dirty or Infected)⁵
8. TBS is from large defects in arteries or veins where the injured vascular wall requires repair with maintenance of vessel patency and which would result in persistent exposure of the EVARREST or SURGICEL to blood flow and pressure during healing and absorption of the product;
9. TBS with major arterial bleeding requiring suture or mechanical ligation;
10. Bleeding site is in, around, or in proximity to foramina in bone, or areas of bony confine.

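### The synopsis keeps pre-term infants out until 28 days past the 37-week point, but neither list of numbered eligibility criteria carries that rule

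*Protocol*

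**What the plan says.** The protocol synopsis, under Study Population, sets two separate lower-age exclusions. One is for newborns: "New born infants (0-27 days from birth) are excluded from this study". The other is for prematurity: "Pre-term births are excluded from this protocol until the subject reaches 28 days from 37 weeks of pregnancy as determined by the investigator". The same paragraph defines the lowest age group as "Infants and toddlers (28 days (1 month) from birth to 23 months".

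The other places that fix the lower age limit read as follows.

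- Inclusion criterion 1, worded alike in the synopsis and in section 4.2, begins "Paediatric subjects aged ≥ 28 days (≥ 1 month) to <18 years". Its item ii adds: "The next 4 subjects to be enrolled will be subjects aged ≥ 28 days to <1 year". Neither sets a condition on gestational age.
- The exclusion criteria (ten items, in the synopsis and again in section 4.3) do not mention pre-term birth, gestational age or corrected age. The nearest is number 6: "Subjects with any pre or intra-operative findings identified by the surgeon that may preclude conduct of the study procedure".
- Protocol section 3 says "the subsequent group will include subjects from 1 month (≥ 28 days from birth) to <1 years of age". The synopsis Study Design paragraph and SAP section 2 also count the 28 days from birth.

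On how eligibility is checked, the Schedule of Events places the inclusion/exclusion review at screening, baseline and surgery. Sections 7.1.1, 7.1.2 and 7.1.3 each describe it as a review of those criteria.

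**The concern.** The newborn exclusion reaches the numbered criteria through the 28-day floor in criterion 1. The pre-term exclusion reaches them nowhere; in the supplied text it appears once, in the synopsis narrative. No screening, baseline or intra-operative step sends the site back to that paragraph. A site could therefore satisfy every numbered criterion and still randomise an infant whom the protocol excludes.

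The data might not reveal the error. The demography listed in section 7.1.1 covers age, sex and race or ethnicity. SAP section 6.1 adds body-size measures and childbearing status. Neither includes gestational age at birth. Medical history is limited to what is relevant, so it need not capture it.

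At stake is a specific protection for the most immature infants, together with the make-up of a very small group that is reported separately (protocol section 8.3.2, SAP section 8.2).

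**Working it through.** The plan gives no figure to reproduce: there is no formal sample size calculation (protocol section 8.1, SAP section 8.2.1), and the question is one of text. The check has three steps.

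**1. Compare the rules.** Take an infant born at G weeks of gestation, with G below 37.

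- Numbered criteria: the age condition is met at day 28 of life.
- Synopsis Study Population: the infant becomes eligible 28 days after the 37-week point, that is at 37 + 4 = 41 weeks from the start of pregnancy. In days of life this is 28 + 7 × (37 − G).
- Gap: [28 + 7 × (37 − G)] − 28 = 7 × (37 − G) days.

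**2. Put in values.** The documents give no distribution of gestational age, so the values of G below are assumptions for illustration.

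| Gestation at birth (weeks) | Day of life, criterion 1 | Day of life, synopsis rule | Gap (days) | Weeks from start of pregnancy at day 28 |
|---|---|---|---|---|
| 36 | 28 | 28 + 7 × 1 = 35 | 7 | 40 |
| 34 | 28 | 28 + 7 × 3 = 49 | 21 | 38 |
| 32 | 28 | 28 + 7 × 5 = 63 | 35 | 36 |
| 28 | 28 | 28 + 7 × 9 = 91 | 63 | 32 |
| 24 | 28 | 28 + 7 × 13 = 119 | 91 | 28 |

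The gap has no natural upper end in the documents; it grows by 7 days for each week of earlier birth.

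**3. Find who can be affected.** Even at 24 weeks the gap closes at day 119, well before the first birthday. Any infant in the gap therefore belongs to the group aged 28 days to under 1 year.

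- Planned size of that group: 4 of 40 = 10%.
- One such infant: 1 of 4 = 25% of the group.
- Analysis: protocol section 8.2.1 and SAP section 5 put every randomised subject in the full analysis set, so the infant would remain in the primary analysis.

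**The case against.** The strongest reply is that nothing is contradictory. The synopsis is part of the protocol, and its Study Population paragraph states the general 28-day floor and then a narrower restriction for pre-term births. Read together they are cumulative: an infant can meet an inclusion criterion and still be excluded. Nor are the numbered lists the only source of eligibility, since section 7.1.3 also requires that the bleeding site be coverable by a stated amount of product, which is not a numbered criterion either. The pre-term rule is expressly left to the investigator's determination. The case report form pages and screening worksheets are not supplied and might carry the rule.

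Much of this stands. The exclusion exists, so a reader should not infer that the protocol as a whole admits these infants; the documents do not support that. Only the protocol's own lists can be shown to omit the rule. But the cumulative reading helps only a site that knows of the restriction, and the specified eligibility check does not point to it. Leaving the determination to the investigator says who decides, not that a decision is needed. Exclusion 6 concerns findings that stand in the way of the study procedure, and birth before 37 weeks is not in itself such a finding.

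Three further inferences are tempting and should not be drawn.

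- *That a wrongly enrolled infant could not be replaced.* The no-replacement sentence in section 7.3 concerns subjects who leave the study early, and 40 is stated as a minimum.
- *That the youngest children are the reason for staged enrolment.* The synopsis says only that the European regulator's paediatric committee required staggering by age, with ongoing safety assessment.
- *That the infant would distort every analysis.* The per-protocol set drops subjects with major deviations affecting the primary endpoint. Whether this deviation would count is not stated, but a route exists.

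**Conclusion.** The concern holds as an internal inconsistency between the synopsis population paragraph and the criteria that sites are told to review. The reach is small: at most the planned infant group, and within it only pre-term infants who have surgery inside the gap and have a qualifying bleeding site. The documents give no basis for estimating how likely that is, so the 25% share is conditional on one such enrolment. The length of the gap rests on the assumed gestations; the formula does not. No power or error-rate claim is affected, because the trial is descriptive.

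It still merits correction, because it concerns who may be exposed, the text can be followed in good faith to the wrong result, and the listed data would not necessarily show that this had happened. This review takes no position on which age rule should govern.

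**What to change.** The sponsor should reconcile the synopsis Study Population paragraph with the synopsis Study Design paragraph, both copies of the numbered criteria (synopsis; sections 4.2 and 4.3), protocol section 3 and SAP section 2. One age rule should appear in both numbered lists and be checked at screening. If the pre-term rule stands, gestational age at birth should be recorded for infants under 1 year so that the check can be verified.

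The cost is one criterion line and one screening field, with matching wording in the SAP. If the pre-term rule is the one retained, some pre-term infants would pass the written criteria a few weeks later than the numbered lists now imply.
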